Mean time response profiles for uric acid concentration raw values and %CFB at each time point for each Treatment period and cohort plotted against time for each Cohort separately with curves for all Treatment periods overlaid on one plot. BLQ values for uric acid concentration will be assigned 0 values for linear scales and 1/10 of LLOQ values for all time points for the graphic representation on log-linear scales only. Actual measured concentrations will be presented on both linear and log-linear scales while %CFB profiles will be presented on linear scale only.

Box plots for each derived PD parameter based on actual measurements and %CFB: CFB_{min}, AUE_{CFBlast}, TA_AUE_{CFBlast} will also be plotted by treatment.

Individual profiles for uric acid concentration absolute values and %CFB will be plotted for each Treatment period and cohort on a separate plot.

9.7. ASSESSMENT OF THE EFFECTS OF SEL-110 (RAPAMYCIN) AND SEL-037 (PEGSITICASE) ON PD PARAMETERS OF URIC ACID

Assessments done outside the assessment windows may be excluded from summarization. This will be determined prior to database lock.

The key PD parameters based on measured values and %CFB %CFB_{min}, AUE_{%CFBlast}, and TA_AUE_{%CFBlast} as well as uric acid concentration and %CFB on day 21 of each treatment period will be analyzed using linear mixed model for the response to SEL-110 dose levels co-administered with either 0.2 or 0.4 mg/kg of SEL-037 (the dose level of SEL-110 for Cohorts 1 and 2 will be assigned as 0). Additionally contribution of SEL-110 to the PD effect of SEL-037 will be tested to compare the following (test - reference). For PD

Statistical Analysis Plan

parameters based on actual measured values baseline concentration of uric acid will be incorporated in the model as covariate.

For Parts A and B following contrasts will be tested:

Cohort 3 Part A vs Cohort 1 Part A
Cohort 5 Part A vs Cohort 1 Part A
Cohort 7 Part A vs Cohort 1 Part A
Cohort 4 Part A vs Cohort 2 Part A
Cohort 6 Part A vs Cohort 2 Part A
Cohort 8 Part A vs Cohort 2 Part A
Cohort 10 Part A vs Cohort 2 Part A
Cohort 12 Part A vs Cohort 2 Part A
Cohort 1 Part A vs Cohort 2 Part A
Cohort 3 Part A vs Part B
Cohort 5 Part A vs Part B
Cohort 7 Part A vs Part B
Cohort 4 Part A vs Part B
Cohort 6 Part A vs Part B
Cohort 8 Part A vs Part B
Cohort 10 Part A vs Part B
Cohort 12 Part A vs Part B

For Part C (cohorts 13, 15, 17) additional contrasts will be:

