Cohort 13 treatment period 4 vs Cohort 11 treatment period 4
Cohort 13 treatment period 5 vs Cohort 11 treatment period 5
Cohort 15 treatment period 4 vs Cohort 11 treatment period 4
Cohort 15 treatment period 5 vs Cohort 11 treatment period 5
Cohort 15 treatment period 4 vs Cohort 13 treatment period 4
Cohort 15 treatment period 5 vs Cohort 13 treatment period 5

Cohort 17 treatment period 4 vs Cohort 11 treatment period 4
Cohort 17 treatment period 5 vs Cohort 11 treatment period 5
Cohort 17 treatment period 4 vs Cohort 13 treatment period 4
Cohort 17 treatment period 5 vs Cohort 13 treatment period 5

Cohort 17 treatment period 4 vs Cohort 15 treatment period 4
Cohort 17 treatment period 5 vs Cohort 15 treatment period 5

Statistical Analysis Plan

Unstructured variance-covariance matrix will be used. If the model cannot converge or unable to make hessian positive definite, compound symmetry or other variance-covariance matrices will be explored and used.

Example SAS code will be:

```
PROC MIXED DATA=data_set_name;  
CLASS subject_id treatment;  
MODEL loge(PD Parameter) = treatment /DDFM=KR;  
RANDOM subject_id / TYPE=UN;  
LSMEANS treatment / DIFFS CL;  
RUN;
```

1. The following hypotheses will be tested:

- $H_{01}: \mu_T/\mu_R \leq 80\%$ vs. $H_{A1}: \mu_T/\mu_R > 80\%$
and
- $H_{02}: \mu_T/\mu_R \geq 125\%$ vs. $H_{A2}: \mu_T/\mu_R < 125\%$

If the 90% confidence interval (CI) for the geometric mean ratio (GMR) is within (80% - 125%) for any of the contrasts for C_{max} , AUC_{0-t} and AUC_{0-inf} , the null hypotheses, that is H_{01} and H_{02} , will be rejected and we will conclude that the Test (T) is equivalent to the Reference (R).

2. If bioequivalence cannot be established in step 1 above, the following hypothesis will be tested to explore noninferiority (1-sided test):

- $H_{01}: \mu_T/\mu_R \leq 80\%$ vs. $H_{A1}: \mu_T/\mu_R > 80\%$

If the lower 90% CI bound for the GMR is greater than 80% for C_{max} , AUC_{0-t} and AUC_{0-inf} , H_{01} will be rejected and we will conclude that the new therapy (T=Test) is no worse than the old therapy (R=Reference).

The formula for calculation of the estimated ratio between the test and reference and the $(1-2*\alpha)*100\%$ CI of the ratio is given below.

Difference = Estimate of difference between test and reference least square means

Statistical Analysis Plan

$$Ratio = 100 \times e^{Difference}$$

(1-2* α)*100% CIs for the Ratio:

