$$Lower = 100 \times e^{(LowerBound (1-2*\alpha)\%CIs for theDifference)}$$

$$Upper = 100 \times e^{(UpperBound (1-2*\alpha)\%CIs for theDifference)}$$

GMR ratio outside equivalence criteria 80-125% will demonstrate (1) dose effect SEL-110; (2) synergy or additive effect of SEL-110 administration on PD by SEL-037. P-values will be generated for all contrasts. Values of $p < 0.05$ will indicate statistical significance of the effect.

The results of the comparisons will be graphically illustrated using box plots for Part A/B and comparison between Part C and B separately.

Correlations between PD endpoints (C_{min} , CFB_{min} , $AUE_{CFBlast}$, and $TA_AUE_{CFBlast}$) and PK parameters (C_{max} , AUC_{0-last} and AUC_{0-inf}) for both SEL-110 and SEL-037 will be explored using Spearman correlation analysis. The correlations for Part C treatment periods will be presented in the separate table.

The correlation between each of these PK (C_{max} , AUC_{0-last} and AUC_{0-inf}) and PD (C_{min} , CFB_{min} , $AUE_{CFBlast}$, and $TA_AUE_{CFBlast}$) parameters will also be explored and presented in a scatter plot with a regression line on it using simple linear regression which will have PK parameter as dependent variable and PD parameter as independent variable. The additional plots will be created for the Part C.

Example SAS code will be:

```
PROC GLM DATA=PKPDDATA;  
MODEL PD_parameter = PK_parameter;  
RUN;
```

Statistical Analysis Plan

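### SAP 9.7 puts %CFBmin, Day-21 %CFB and Day-21 urate on a log/GMR scale, although %CFB is signed and BLQ urate is coded 0, so falls and BLQ values have no log

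*SAP*

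**What the plan says.** SAP 9.7 takes three summary parameters (%CFBmin, AUE%CFBlast, TA_AUE%CFBlast) into a dose-response analysis whose scale is not stated. Two Day-21 measures join them: "as well as uric acid concentration and %CFB on day 21 of each treatment period will be analyzed using linear mixed model". It then adds contrasts: "Additionally contribution of SEL-110 to the PD effect of SEL-037 will be tested to compare the following (test - reference"). For parameters based on measured values, "baseline concentration of uric acid will be incorporated in the model as covariate".

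The only model shown for the contrasts is "MODEL loge(PD Parameter) = treatment /DDFM=KR", under a label calling it an example. The text then defines the result as 100 times the exponential of the difference in least-squares means. Equivalence holds if the 90% CI of the GMR "is within (80% - 125%) for any of the contrasts for" Cmax, AUC0-t and AUC0-inf. The closing interpretation turns to PD: "GMR ratio outside equivalence criteria 80-125% will demonstrate (1) dose effect SEL-110", or a synergistic or additive effect of SEL-110 on the PD of SEL-037.

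The endpoints are defined elsewhere:
- SAP 9.1 defines %CFB as change from baseline divided by baseline, times 100, with no absolute value or sign reversal. SAP 9.3 defines %CFBmin as its minimum.
- SAP 9.3 specifies an absolute value for AUE%CFBlast but omits those words for TA_AUE%CFBlast.
- SAP 9.3.1 and 9.4 set BLQ urate to zero at all time points.
- SAP 9.4 plans a geometric mean and geometric CV for CFBmin and %CFBmin.

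**The concern.** Zero and negative numbers have no logarithm. An undefined response is missing, and a mixed model omits it. For the %CFB endpoints the plan as written therefore discards the responders. For Day-21 urate it discards the BLQ subjects and compares only those who still have measurable urate. A SEL-110 benefit that consists of more subjects staying BLQ would not enter that comparison.

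PD is a secondary objective, and these contrasts are one of the routes by which the SAP judges the contribution of SEL-110. The authors met the same problem elsewhere. SAP 9.6 assigns BLQ urate "1/10 of LLOQ values for all time points for the graphic representation on log-linear scales only" and plots actual concentrations on both scales "while %CFB profiles will be presented on linear scale only". SAP 8.7 leaves its parameters unlogged so that a zero dose can enter. SAP 9.7 has no corresponding rule.

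**Working it through.** The SAP gives no power or sample-size figure for these contrasts, so there is nothing to reproduce. The check concerns which values have a log, and what is lost.

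**1. Which values have a log.** %CFB = 100 × (value − baseline)/baseline. At the entry minimum of 6 mg/dL (screening, Protocol 7.1):
- BLQ coded 0: %CFB = −100; neither %CFB nor urate has a log.
- Urate 0.1: %CFB = 100 × (0.1 − 6)/6 = −98.3; no log of %CFB.
- Urate 1.0: %CFB = −83.3; no log of %CFB, while ln(1.0) = 0 exists for urate.
- Urate 6.6: %CFB = +10; ln(10) = 2.303.

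Only a rise in urate gives a usable %CFB. Protocol 4.3.2.1 reports all 22 SEL-037 subjects below quantification from Study Day 2. Protocol 4.3.2.3 reports all SEL-212 subjects below 0.1 mg/dL within 24 hours. On such data %CFBmin has no log for anyone.

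**2. Number of contrasts.** Parts A/B: 9 between cohorts + 8 Part A versus Part B within cohort = 17. Part C: 6 + 4 + 2 = 12. Total 29, of which 21 are between cohorts. Eight compare SEL-212 with SEL-037 alone (Cohorts 3, 5, 7 versus 1; Cohorts 4, 6, 8, 10, 12 versus 2).

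**3. Sensitivity to the unstated BLQ handling.** Take invented Day-21 values: test six BLQ plus 6.0, 6.8, 5.1, 7.4; reference 7.1, 6.4, 8.0, 5.5, 6.9, 7.7, 4.8, 6.2, 0.9 and one BLQ. Dropping BLQ leaves 4 versus 9 subjects, with geometric means 6.26 and 5.21 and GMR 120.2%. Substituting LLOQ/10 up to LLOQ, with an assumed LLOQ of 0.05 to 0.5 mg/dL, gives 3.3% to 33.3%. The choice alone moves the result from inside 80-125% to far outside it.

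**4. Illustration of lost information, Day-21 urate.** BLQ shares are not in the documents. As proxies I use Day-30 persistence of effect: 17/31 = 54.8% with SEL-212 (Protocol 10.1.1), and 1/22 = 4.5% to 2/22 = 9.1% with SEL-037 alone (Protocol 4.3.2.1). Non-BLQ values are assumed lognormal around 6 mg/dL in both cohorts, with CV 30%.
- Usable test records at n = 20: 20 × (1 − 0.548) = 9.0.
- GMR among quantifiable subjects: 6/6 = 1.00. Ratio of all-subject means: 0.452/0.955 = 0.47 to 0.452/0.909 = 0.50.
- Simulated power (two-sided 0.05, pooled t-tests, one record per subject, no covariate):

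| Cohort sizes | Log, BLQ dropped | Untransformed, BLQ = 0 |
|---|---|---|
| 20 v 20 | about 5% | 82-91% |
| 20 v 6 | about 5% | 45-53% |

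**5. Relaxing the assumption that every controlled subject is BLQ.** If a quarter to a half of controlled subjects are quantifiable at 0.1-1.0 mg/dL, the log model at 20 v 20 recovers to about 37-77% power, with GMR about 0.6 to 0.4. With equal BLQ shares in the two cohorts there is no distortion.

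**The case against.** The strongest reply is that the code is only an example, that the 90% CI rule names PK parameters, and that a programmer would notice a failing %CFBmin model at once. The first two facts are correct, but neither rescues the plan. The exponential back-transform and the closing 80-125% sentence are plan text, they concern PD, and both need logs. A failure on %CFBmin would indeed be visible. The loss of BLQ urate values could pass unnoticed.

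The planned geometric statistics for CFBmin could also mean that a magnitude was intended. That is possible, but SAP 9.3 writes an absolute value for AUE and not for CFBmin or %CFBmin.

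The objection to the size stands in large part:
- The 55% versus 5-9% scenario describes only the 8 SEL-212 versus SEL-037-alone contrasts. It does not describe Cohort 1 versus 2, the Part A versus Part B contrasts, or Part C. In Part C no reference is a SEL-037-only cohort, and subjects reach Periods 4-5 only after a Day-21 urate of at most 1.0 mg/dL.
- Cohorts 1 and 2 are closed, and their cohort rule ends enrolment after 5 individual stops, so a reference of 20 is doubtful.
- A log-model GMR of exactly 1.00 follows from assuming that no controlled subject is quantifiable.
- The proxies are Day-30 counts of an effect not defined as BLQ.

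A reader might infer that SAP 9.7 has no workable test of SEL-110 at all. The documents do not support that. AUE%CFBlast is in the same model, is an absolute value, and can be logged if BLQ samples enter as 0 and the area is not cut at the last quantifiable value. The dose-response analysis has no stated scale.

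**Conclusion.** The plan is wrong as written for three endpoints. That conclusion rests on definitions in the SAP and needs no assumption about the data beyond urate falling and some values being BLQ. %CFBmin and Day-21 %CFB fail in all 29 contrasts, except for subjects above baseline. The geometric mean and CV of CFBmin and %CFBmin in SAP 9.4 are undefined for the same reason.

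For Day-21 urate the mechanism is certain and the size is not. It depends on the LLOQ and on how BLQ shares differ between cohorts. The power figures are illustrations and should not carry the weight of the point. A reader might take them as a forecast that the log analysis will miss a SEL-110 effect or declare false equivalence at a known rate. The documents give no basis for such a rate, and the 90% CI equivalence rule is stated only for Cmax and AUC. Nor can one assume a nadir near −100% in every period, because the supporting data are from single doses.

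Not affected: AUE%CFBlast (on the condition above), the dose-response analysis, arithmetic summaries, box plots, counts below 6 mg/dL, the Day-21 table split at 1.0 mg/dL in SAP 10.4, and the primary safety analysis. This should be fixed before analysis.

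**What to change.** 1. Analyse %CFBmin and Day-21 %CFB untransformed in the planned mixed model. Report mean differences with CIs and do not apply the GMR rule. A baseline urate covariate is optional here, because SAP 9.7 requires it only for parameters based on measured values.
2. Analyse Day-21 urate untransformed with BLQ = 0, keeping all observed subjects, with the baseline covariate that SAP 9.7 requires and the planned subject effect. As sensitivity, add a rank test with BLQ tied lowest for the 21 between-cohort contrasts.
3. Keep the log/GMR scale for strictly positive parameters only, and name the PD endpoints in the decision rule in place of Cmax and AUC.
4. Drop geometric statistics for CFBmin and %CFBmin in SAP 9.4.
5. In SAP 9.3, write absolute value for TA_AUE%CFBlast, and integrate AUE to the last observed sample with BLQ = 0.

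The cost is SAP wording and reprogramming of the 9.4 and 9.7 tables; no new data are needed. Results for these endpoints become differences rather than GMRs. Some power is lost when BLQ shares are equal: with 20 per cohort, 5 versus 6 mg/dL, CV 30% and 10% BLQ in both, simulated power is 44% for the log model, 33% for the rank test and 24% untransformed.

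### The pharmacodynamic mixed model in SAP 9.7 cannot be fitted as coded, has no period effect for its pooled Part A contrasts, and leaves treatment undefined

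*SAP*

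**What the plan says.** SAP 9.7 fits a linear mixed model to the key uric acid parameters and to Day 21 uric acid in each treatment period. The code, introduced by "Example SAS code will be", has "CLASS subject_id treatment", then "MODEL loge(PD Parameter) = treatment /DDFM=KR", then "RANDOM subject_id / TYPE=UN", and one `LSMEANS` statement asking for all differences.

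The surrounding text adds two things:
- For parameters based on measured values, "baseline concentration of uric acid will be incorporated in the model as covariate".
- On estimation failure: "If the model cannot converge or unable to make hessian positive definite, compound symmetry or other variance-covariance matrices will be explored and used".

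Period appears in neither the text nor the code as a model term, and the levels of treatment are not defined.

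Twenty-nine contrasts are listed:
- 9 compare cohorts over Part A, for example "Cohort 3 Part A vs Cohort 1 Part A". Eight of these set a SEL-212 cohort against Cohort 1 or 2; the ninth is Cohort 1 against Cohort 2.
- 8 compare Part A with Part B within a cohort.
- 12 involve Part C and compare cohorts within Period 4 or within Period 5.

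SAP 9.1 identifies Part A with Periods 1-3 and Part B with Periods 4-5. Protocol 6.3.1 makes further dosing depend on Day 21 uric acid. Cohorts 1-2 stop at 6 mg/dL or above, or above 50% of baseline; the SEL-212 cohorts continue only at 1.0 mg/dL or below.

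**The concern.** The covariance statement puts the unstructured matrix in the wrong place. The evident purpose is to model the correlation among one subject's periods. Without `SUBJECT=`, the code asks instead for a free covariance between every pair of subjects. When that fails, the analyst must choose a structure after seeing the failure, and the one alternative that the plan names also fails.

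The missing period effect is a separate matter. A subject contributes between one and three Part A records, and the number depends on the outcome under rules that differ between the two sides of eight contrasts. If uric acid response drifts over periods, cohorts with different mixes of periods will differ even when SEL-110 does nothing. A drift is plausible: protocol 4.5.1 suggests that the first period may be critical for preventing antibodies.

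The stakes are stated in SAP 9.7 itself. A geometric mean ratio (GMR) outside 80-125% is to be read as demonstrating a SEL-110 dose effect or synergy, and p below 0.05 as significance.

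**Working it through.** SAP 9.7 gives no figure of its own to reproduce.

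**1. Covariance parameters.** An unstructured matrix of dimension q has q(q+1)/2 parameters. SAP 3.7 plans about 100 subjects in Parts A and B.
- As coded, across subjects: 100 × 101 / 2 = 5,050, against at most 100 × 3 = 300 records in Part A or 100 × 5 = 500 over five periods.
- Across a subject's periods: 3 × 4 / 2 = 6 for three periods, 5 × 6 / 2 = 15 for five.

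A simulated check used 24 subjects, 3 periods and 4 treatments:
- Unstructured: 24 × 25 / 2 + 1 = 301 parameters, 72 − 4 = 68 error contrasts, and an expected-information matrix of rank 211. The REML log-likelihood rose from 15.3 under variance components to 34.5 as the matrix collapsed to rank 1.
- Compound symmetry: the log-likelihood stayed at 15.338 for a common covariance anywhere from 0 to 100. A covariance shared by all subjects is a shift common to every record, and the treatment means absorb it. The treatment differences do not depend on it, but the Hessian is singular, which is the plan's own reason for abandoning a structure.
- Variance components: an ordinary random intercept, estimable.

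**2. Part A contrasts between cohorts.** Assumptions, none in the documents: 80% and 60% of one cohort reach Periods 2 and 3, against 40% and 20% of the other; response is multiplied by a factor f per period; there is no cohort effect. Retention enters as fixed shares, so this isolates the effect of period mix.

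Ignoring within-subject correlation, the mean period index (Period 1 = 0) is (0.8 + 2 × 0.6) / (1 + 0.8 + 0.6) = 0.833 in one cohort and (0.4 + 2 × 0.2) / (1 + 0.4 + 0.2) = 0.500 in the other. The null ratio is therefore f^0.333. The last two columns use generalised least squares with assumed between-subject SD 0.5 and residual SD 0.4 on the log scale.

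| f | f^0.333 | GLS, no period term | GLS, with period |
|---|---|---|---|
| 1.1 | 103.2% | 103.8% | 100.0% |
| 1.25 | 107.7% | 109.1% | 100.0% |
| 1.5 | 114.5% | 117.1% | 100.0% |
| 2.0 | 126.0% | 131.0% | 100.0% |

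Equal retention gives 100.0% at every f. Swapping the two retention patterns inverts the ratio; for example 1 / 1.31 = 76%.

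A simulation with response-driven continuation gives a sense of the test's behaviour. It assumed between-subject SD 1.0, within-subject SD 0.7, a trend of ±0.4 SD per period, continuation cut-offs of 1.0 and 0.0 SD, and known variances. The spurious contrast was about 0.10-0.14 SD. Two-sided type I error at a nominal 5% was about 3% (rising trend) and 8.5% (falling) with 20 per cohort, and about 2% and 5% with 6 per cohort. With a period term the bias was about zero.

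**3. Part A versus Part B within a cohort.** With complete data the mean period index is (0 + 1 + 2) / 3 = 1 in Part A and (3 + 4) / 2 = 3.5 in Part B. The null ratio is f^(1 − 3.5). At f = 1.1 this is 78.8%, already outside 80-125%. Adding period within one cohort does not help: the design has 6 columns and rank 5. Adding a cohort whose treatment does not change, with period effects shared, gives 7 columns and rank 7.

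**4. Coding of treatment.** The Part C contrasts need levels that carry both cohort and period. The Part A contrasts need levels that pool Periods 1-3. One `LSMEANS` / `DIFFS` call on one treatment factor cannot return both, and no `ESTIMATE` statements are given.

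**The case against.** The strongest reply is that the code is labelled an example, the text supplies the baseline covariate, and the plan foresees non-convergence and allows other structures. Part of this stands. Variance components falls within those other structures and is estimable, so a reader should not conclude that no permitted model can be fitted. Nor does the plan drop baseline adjustment: the text requires it for measured-value parameters and only the code omits it. Not promising it for percent-change parameters is defensible, since those already divide by baseline. The example label does not answer the period point, because the text has no period term either.

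A reader might also infer that every contrast in 9.7 is confounded with period, or that the covariance error causes the period problem. The documents support neither. The 12 Part C contrasts are matched on period, the Part A contrasts are biased only if there is both a period effect and unequal retention, and the defects are independent of one another.

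It is fair to add that the sizes above rest on invented inputs, that error inflation appeared for one trend direction and in the larger cohorts, and that Cohorts 1 and 2 are closed and subject to a five-subject stopping limit, so 20 per reference cohort is doubtful. Pharmacodynamics is also a secondary objective; safety is primary.

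**Conclusion.** The point holds as three separate defects, and should be corrected before the analysis is run.

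1. The covariance statement is not estimable as written. Compound symmetry in the same statement is not identified. Of the structures checked, only a random intercept works. This rests on no assumption beyond the planned sample size.
2. The absence of a period effect can bias the eight Part A contrasts that cross the two continuation rules. The illustrative null ratio of 104%-131% depends on assumed retention and period factors. The documents give neither, nor the direction of any retention difference, so it shows what is possible and is not a forecast. The eight Part A versus Part B contrasts are aliased with period by design, whatever the retention. The 12 Part C contrasts are not affected by this point.
3. Treatment is undefined, the single `LSMEANS` call cannot yield both sets of contrasts, and the code disagrees with the text on baseline.

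**What to change.** - Replace the random statement with `REPEATED period / SUBJECT=subject_id TYPE=UN`. Name the fallback in advance: compound symmetry, or a random intercept, each with `SUBJECT=subject_id`.
- Add period as a fixed effect.
- Define treatment as cohort, with cohort-by-period terms only where cells hold data, and write an `ESTIMATE` statement for each listed contrast.
- Put baseline uric acid in the code for measured-value parameters.
- Report the Period 1 cohort contrasts beside the pooled ones. All dosed subjects enter Period 1, so this check is free of response-driven continuation. It should not replace the pooled contrasts, since the objectives concern multiple infusions.
- Label the Part A versus Part B contrasts descriptive, or borrow period effects from a cohort whose treatment does not change and that has data in Periods 4-5.

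The cost is SAP wording, code and some degrees of freedom. With 6-20 subjects per cohort and response-driven stopping, late cells will be sparse and some cohort-by-period means may not be estimable; the SAP should say how those will be reported.

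### The single lower-bound non-inferiority rule in SAP 9.7 faces the wrong way for Day-21 uric acid once that section's own endpoints are substituted for the PK parameters it names

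*SAP*

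**What the plan says.** SAP 9.7 covers the effect of SEL-110 and SEL-037 on uric acid. Beside %CFBmin (the minimum percent change from baseline), AUE and TA_AUE, it states that "uric acid concentration and %CFB on day 21 of each treatment period will be analyzed using linear mixed model". Cohort contrasts follow: "Additionally contribution of SEL-110 to the PD effect of SEL-037 will be tested to compare the following (test - reference"). The example code is "MODEL loge(PD Parameter) = treatment /DDFM=KR", and the difference in least-squares means is back-transformed to a test/reference ratio.

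Two steps are given. Step 1 is equivalence: the 90% interval must lie within 80–125%. If that fails, "the following hypothesis will be tested to explore noninferiority (1-sided test"), with null hypothesis μT/μR ≤ 80%. The decision reads "If the lower 90% CI bound for the GMR is greater than 80% for" Cmax, AUC0-t and AUC0-inf, in which case "we will conclude that the new therapy (T=Test) is no worse than the old therapy (R=Reference"). No reversed version is given for any endpoint.

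Elsewhere lower uric acid is the favourable direction. The secondary objective in SAP 3.2 concerns reducing it, SAP 9.3 and 9.6 count subjects below 6 mg/dL, and protocol 6.3.1 makes a Day-21 value of 1.0 mg/dL or less the condition for the next dose in the SEL-110 cohorts.

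**The concern.** A non-inferiority margin has to sit on the harmful side. For an endpoint where larger is better, that is the lower side, and an 80% lower limit is coherent. For Day-21 uric acid concentration, harm is an increase, so the upper bound has to be limited. The step 2 rule limits only the lower bound, so on this endpoint it guards against too much benefit.

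What is at stake is the label attached to the PD contrasts. They include SEL-212 against SEL-037 alone, and Part C regimens with less SEL-110 against one with more (Cohort 17 vs 13, Cohort 15 vs 13). A statement of no worse would be read as support for the lower-dose regimen, yet on this endpoint it becomes more likely as uric acid rises.

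**Working it through.** **Inputs from the documents.** Limits 80% and 125% and a 90% interval (SAP 9.7); log scale and test/reference ratio (SAP 9.7); 6–20 subjects per cohort in Parts A and B (SAP 3.7). Part C allows up to 40 over three cohorts, about 13 each if split evenly (40/3 = 13.3).

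**Assumed.** The documents give no SD for log Day-21 uric acid, so 0.5, 1.0 and 2.0 are used. The wide end is plausible. Protocol 4.3.2.3 reports levels below 0.1 mg/dL within 24 hours of SEL-212, and entry requires at least 6 mg/dL. For a cohort split between 0.1 and 6 mg/dL, ln 60 = 4.09, so the log-SD is 4.09 × √(0.5 × 0.5) = 2.0 for a 50/50 split and 4.09 × √(0.8 × 0.2) = 1.6 for 80/20.

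**Consistency of the limits.** The SAP states no power or sample size for this test, so there is no figure to reproduce. The limits are coherent: 1/0.80 = 1.25, and a 90% interval corresponds to one-sided alpha 0.05.

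**Side for each endpoint (SAP 9.3 definitions).**
- AUE and TA_AUE: areas of change taken as absolute values, so larger means more lowering. The lower-bound rule fits.
- Day-21 concentration: larger is worse. The lower-bound rule is reversed.
- %CFB and %CFBmin: negative when uric acid falls, so neither a log nor a ratio rule applies.

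**Interval for two cohorts of n each.** GMR × exp(± t(0.95, 2n−2) × SD × √(2/n)).

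With n = 10 and SD = 0.5, the exponent is 1.734 × 0.5 × √0.2 = 0.388, and exp(0.388) = 1.474.
- Observed doubling: 200/1.474 to 200 × 1.474 = 136–295%. The lower bound exceeds 80%, so the label is no worse.
- Observed halving: 50/1.474 to 50 × 1.474 = 34–74%. It fails.

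The halving result is general: the lower bound lies below the point estimate of 50%, so it cannot exceed 80% at any n or SD. An observed doubling passes when SD < ln(2/0.8) / [t × √(2/n)]:
- n = 6: 0.916/1.046 = 0.88
- n = 10: 0.916/0.775 = 1.18
- n = 20: 0.916/0.533 = 1.72

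**Probability of the no-worse label.** With δ = [ln(true GMR) − ln 0.8] / [SD × √(2/n)], this is P(noncentral t with 2n−2 df and noncentrality δ exceeds t(0.95, 2n−2)). For a doubling at n = 10 and SD = 1.0, δ = 0.916/0.447 = 2.05, which gives 0.628.

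| n per cohort | True doubling, SD 0.5 / 1.0 / 2.0 | True halving, SD 0.5 / 1.0 / 2.0 |
|---|---|---|
| 6 | 0.904 / 0.434 / 0.183 | 0.001 / 0.008 / 0.021 |
| 10 | 0.989 / 0.628 / 0.255 | <0.001 / 0.004 / 0.016 |
| 20 | 1.000 / 0.885 / 0.412 | <0.001 / 0.001 / 0.009 |

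**Reversed side (upper bound below 125%).** Because ln(1.25/0.5) = ln(2/0.8) = 0.916, the two columns swap exactly. At n = 10 a true halving would pass 0.989 / 0.628 / 0.255 of the time, and a true doubling <0.001 / 0.004 / 0.016.

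The baseline covariate and the repeated periods of the SAP model are left out of this check.

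**The case against.** **The rule does not name Day-21 uric acid.** It names Cmax, AUC0-t and AUC0-inf, and the same section later lists Cmax, AUC0-last and AUC0-inf as PK parameters. The text may simply be carried over from an exposure analysis, where a lower-bound rule is sensible. This stands in part: the error visible on the page is the parameter list, and the reversed side appears only after substitution. But the section's title, contrasts and code all concern PD parameters, so substitution is the natural repair, and repairing the names alone would leave the side wrong for this endpoint.

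**Joint reading.** The rule joins its parameters with *and*. If all 9.7 endpoints had to pass together, a cohort losing uric acid control would tend to fail on AUE. A reader might infer that nothing at all limits harm; on a joint reading that is too strong. The joint reading does not rescue the rule, however, because a cohort that halves Day-21 uric acid would still fail.

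**Other outputs.** P-values, box plots and the tables of subjects below 6 mg/dL would show a rise beside any label. That is fair. The further statement in 9.7 that a ratio outside 80–125% demonstrates an effect gives no correction, because it has no direction and treats a doubling and a halving alike.

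**Stakes.** A reader might infer that the rule affects continued dosing, since Day-21 uric acid decides it. The documents do not support that. The dosing rule in protocol 6.3.1 uses each subject's own value; the contrasts are run after all subjects finish (SAP 2.2), and no interim analysis is planned (SAP 12). Step 2 is itself described as exploring non-inferiority.

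**Conclusion.** The rule is wrong as written for Day-21 uric acid concentration once 9.7's own endpoints are put into it; for AUE and TA_AUE the side is right. That an observed halving can never be called no worse needs no assumption about spread or cohort size.

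A reader might infer that a cohort with much higher uric acid would routinely be declared no worse. The documents do not support that without a value for the spread. A true doubling is so labelled about 99% / 63% / 25% of the time at log-SD 0.5 / 1.0 / 2.0 with 10 per cohort, 90% / 43% / 18% with 6, and 100% / 89% / 41% with 20. A true halving is so labelled about 2% of the time at most. These figures assume equal parallel cohorts, log-normal values, one contrast and no covariate adjustment.

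The defect affects an exploratory conclusion on a secondary PD objective. It does not touch the primary safety objective or individual dosing decisions.

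**What to change.** In SAP 9.7:
- Replace the parameter names in steps 1 and 2 with the section's PD endpoints.
- State the step 2 side for each endpoint. For AUE and TA_AUE, keep H0: μT/μR ≤ 80% and conclude no worse if the lower 90% bound exceeds 80%. For Day-21 uric acid concentration, use H0: μT/μR ≥ 125% and conclude no worse only if the upper 90% bound is below 125%.
- Say that TA_AUE based on %CFB is an absolute value; its entry in 9.3 does not, although the neighbouring AUE entry does.
- Do not apply the log-ratio rule to %CFB or %CFBmin; analyse these as differences.
- Specify a non-zero value for uric acid below the quantification limit before logging. SAP 9.3.1 sets such values to zero, and the one-tenth-LLOQ substitution in 9.6 is for log-scale graphs only.

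The cost is SAP wording and code, with no new data. Fewer statements of no worse should be expected.
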